8.2.7 Withdrawal criteria

The patient or the parents may withdraw from the study at will at any time. Besides, early discontinuation may occur for the following reasons:

- Patient withdrawal (opposition)
- Lost to follow-up
- Death

In case of withdrawal, the physician should attempt to collect any outstanding data. The primary reason for discontinuation should be specified in the Case Report Form (CRF).

8.2.8 Visit procedures

8.2.8.1 Study flow chart

Table 9 Study flow-chart

	Baseline (M0)	M6	M12	M18	M24	M30	M36	M42	M48
Inclusion/Exclusion criteria	X								
Socio-demographic characteristics									
Year of birth	X								
Sex	X								
Education, school level and educational measures	X	X	X	X	X	X	X	X	X
Clinical characteristics									
Age of onset of puberty	X								
Date of onset of menstruations (female only)	X								
Tanner stage	X	X	X	X	X	X	X	X	X
Comorbidities of interest not related to NS	X								
Pulse rate	X	X	X	X	X	X	X	X	X
Blood pressure (diastolic, systolic)	X	X	X	X	X	X	X	X	X
Echocardiogram parameters	X		X		X		X		X
Corrected QT interval (QTc) (measured by electrocardiogram (ECG))	X		X		X		X		X
Complete blood count (CBC)	X	X	X	X	X	X	X	X	X
Haemostasis parameters	X								
IGF-1 level	X	X	X	X	X	X	X	X	X
IGFBP-3 level	X								
TSH level	X								
FT4 level	X								
HbA _{1c} level	X		X		X		X		X
Fasting insulin blood level	X		X		X		X		X
Fasting glucose blood level	X		X		X		X		X
Fasting total cholesterol	X		X		X		X		X

	Baseline (M0)	M6	M12	M18	M24	M30	M36	M42	M48
Fasting triglycerides	X		X		X		X		X
Fasting HDL level	X		X		X		X		X
Fasting LDL level	X		X		X		X		X
Fasting Ratio total cholesterol/ HDL level	X		X		X		X		X
Parameters of gonadal function (inhibin B, AMH, LH, FSH, oestradiol / testosterone)	X		X		X		X		X
NS characteristics									
Auxological characteristics									
Gestational age at birth	X								
Head circumference at birth, at 1 year, at 2 years and 3 years of age	X								
Weight at birth, at 1 year, at 2 years and 3 years of age	X								
Length at birth, at 1 year, 2 years and 3 years of age	X								
Height velocity in the first year/ 6 months preceding Norditropin® start	X								
Weight at Norditropin® start	X	X	X	X	X	X	X	X	X
Height at Norditropin® start	X	X	X	X	X	X	X	X	X
Father 's height	X								
Mother's height	X								
Adult height (NAH)	X								
Bone age	X		X		X		X		X
Diagnosis									
Familial form of Noonan	X								
Parent affected	X								
Age of clinical diagnosis of NS	X								
Date of molecular diagnosis	X								
Molecular diagnosis (Type of NS-related genes mutated, and variant identified)	X								
NS comorbidities									

	Baseline (M0)	M6	M12	M18	M24	M30	M36	M42	M48
NS comorbidities	X	X	X	X	X	X	X	X	X
Therapeutic care									
Norditropin® treatment patterns									
Date of start	X								
Dose at start	X								
Dose titration		X	X	X	X	X	X	X	X
Dose at the end of treatment		X							
Frequency of injections per week	X	X	X	X	X	X	X	X	X
Treatment modifications (change in dosage, temporary stop)		X	X	X	X	X	X	X	X
Date of end of treatment		X							
Reasons for treatment modifications		X	X	X	X	X	X	X	X
Other GH treatments									
Previous GH treatments (type, dose at start and total duration)	X								
GH treatment following Norditropin® (type, dose and date of initiation)		X							
Other NS treatments									
Concomitant medications (with a focus on ADHD* medications including methylphenidate, cardiac medications, thyroid hormones, sex steroids comprising testosterone and oestrogens)	X	X	X	X	X	X	X	X	X
HRQoL									
PedsQL	X		X		X		X		X
Safety									
SAR, AR, SAE and AE		X	X	X	X	X	X	X	X
Pregnancy		X	X	X	X	X	X	X	X

*ADHD: Attention deficit hyperactivity disorder

8.2.8.2 Study visits

The physician should keep a patient enrolment log. The routine treatment of the patients enrolled into the registry should not be influenced by recruitment. Therefore, the data collected is only what is collected as part of standard routine and missing data is expected. This registry will collect data on patients during biannual visits (every 6 months) for 4 years, with possibility of extension for patients who did not reach adult height, starting from the inclusion (D0). As so 8 follow-up study visits (M6; M12; M18; M24; M30; M36; M42; M48) are anticipated. The frequency of the visits is based on actual recommendations on the follow-up of NS patients treated with GH therapy for short stature. Nevertheless, this frequency remains determined by the study site/enrolling physician.

D0 (Baseline-Inclusion)

At the initial visit, children and/or their parents will be informed about the registry objectives and overall requirements, and an information notice will be given to them by the enrolling physician. If they do not oppose to the collect and process of their medical data and are eligible to the registry, the physician will enrol the patient to the study and collect his/her data. Medical data will be collected by physicians using an electronic case report form (eCRF) for each patient. QoL data are patient reported outcomes (PROs) and as so will be collected directly from patients using a questionnaire.

Follow-up visits (from M6 until M48 every 6 months)

During follow-up visits, enrolling physicians will assess patients within clinical routine standard of care. QoL data will be collected annually (D0, M12, M24, M36 and M48) on incident patients.

All drug related adverse reactions (ADR), serious adverse drug reactions (SADR), serious adverse events (SAE) and adverse events (AE) will be recorded and described up to the end of growth development or end of follow-up, if earlier.

8.2.9 Assessments for safety and growth

Growth evolution

Growth evolution endpoints of GH treatment (Norditropin[®]) will be assessed by collecting height characteristics at baseline and at each follow-up visit to derive height variation in SDS, bone age, and height velocity values.

Safety

All children who received at least one administration of Norditropin[®] will be included in the evaluation for safety. All serious adverse events (SAE), serious adverse drug reactions (SADR), drug related adverse reactions (ADR) and adverse events (AE), regardless of causal relationship and seriousness criteria, and pregnancies that occur during follow-up will be recorded, reported and described.

At every follow-up visit, the enrolling physician ascertains the occurrence of ADR, SADR, SAE, AE and pregnancies. The physician must report ADR, SADR, SAE and AE using the NIS Safety Form to Novo Nordisk or to [REDACTED] within 3 calendar days of the physician's knowledge of the event. Pregnancy must be reported on the paper pregnancy form within 14 calendar days of the physician's first knowledge of the pregnancy.

Definitions and further details about ADR, SADR, SAE, AE and pregnancies are provided [10](#) section.

8.2.10 Other assessments

Socio-demographic characteristics

- Sex (baseline)
- Age at start of Norditropin[®] treatment in years (baseline)

Clinical characteristics

- Age at puberty onset (at baseline or one of the follow-up visit)
- Age at onset of menstruations (female only) (at baseline or one of the follow-up visit)
- IGFBP-3 level (baseline)
- TSH level (baseline)
- FT4 level (baseline)
- Haemostasis parameters

Norditropin[®] treatment patterns

- Date at start (baseline)
- Dose of Norditropin[®] at treatment start in mg/k/day (baseline)
- Date at the end of treatment (at one of the follow-up visit)
- Dose of Norditropin[®] in mg/k/day at the end of follow-up (at one of the follow-up visit)

GH treatment history

- Type and number of previous GH treatments (baseline)
- Duration of GH treatment before Norditropin[®] in years (baseline)
- Dose of GH treatment before Norditropin[®] in mg/kg/day (baseline)
- Type of GH treatment following Norditropin[®] (at one of the follow-up visit)
- Date of start of GH treatment following Norditropin[®] (at one of the follow-up visit)
- Dose of GH treatment following Norditropin[®] in mg/kg/day (at one of the follow-up visit)

Auxological characteristics

- Age at gestational age in weeks (baseline)
- Weight at birth, 1 year, 2 years and 3 years of age in kg (baseline)

- Length at birth, 1 year, 2 years and 3 years of age in cm (baseline)
- Head circumference at birth, 1 year, 2 years and 3 years of age in cm (baseline)
- Height velocity in the first year/six months preceding Norditropin® treatment start
- Mother's height in cm (baseline)
- Father's height in cm (baseline)
- AH in SDS (at one of the follow-up visit)

Diagnosis

- Familial form of Noonan (baseline)
- Parent affected (baseline)
- Age of clinical diagnosis of NS (baseline)
- Molecular diagnosis performed (at one of the follow-up visit)
- Date of molecular diagnosis (at one of the follow-up visit)
- Molecular diagnosis (type of NS-related genes mutated, and variant identified) (at one of the follow-up visit)

NS comorbidities

- Type and number of NS comorbidities (baseline)

Health-Related Quality of Life (PROs): PedsQL

HRQoL will be assessed on incident patients only. They will be asked and their parents to complete the PedsQL questionnaire annually.

The PedsQL is a widely used 23-items generic questionnaire that assesses the HRQoL in children and adolescents (2-18 years) from the child- and parent perspective. This questionnaire is multidimensional measuring physical (8 items), emotional (5 items), social (5 items) and school functioning (5 items). Responses are assessed using a five-point Likert scale (0 = never a problem; 1 = almost never a problem; 2 = sometimes a problem; 3 = often a problem; 4 = almost always a problem) (3). The PedsQL questionnaire is applicable for healthy school and community populations, as well as paediatric populations with acute and chronic health conditions, which proved satisfactory internal consistency reliability ($\alpha = 0.88$ child, 0.90 parent report for the total scale score) (4). The PedsQL total score is computed as the sum of all the items. Items will be transformed to 0-100 scale so that higher scores indicate better HRQoL

Evaluation of PedsQL will be performed at baseline visit and at annual follow-up visits. Baseline PedsQL score will be compared with those taken after 12, 24, 36 and 48 months of Norditropin® treatment.

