Number of modifications (change in dosage/ temporary stop)	From start of Norditropin® treatment until end of follow-up	Count of events
Reasons for treatment modifications	From start of Norditropin® treatment until end of follow-up	NA
Duration of temporary stop	From start of Norditropin® treatment until end of follow-up	Months

Title of endpoint	Time frame	Unit
Total duration of Norditropin [®] treatment	From start of Norditropin [®] treatment until end of follow-up	Years
Total cumulative dose of Norditropin [®] treatment	From start of Norditropin [®] treatment until end of follow-up	mg/kg
Other NS treatments		
Type and number of concomitant treatments	At all visits	Count of events
Type and number of concomitant treatments linked to an adverse event	At all visits	Count of events

Secondary objective-4: To describe the NS in terms of auxological characteristics, diagnosis and NS comorbidities.

The endpoints related to the secondary objective-4 are listed in [Table 6](#).

Table 6 Secondary endpoints in relation to secondary objective 4

Title of endpoint	Time frame	Unit
Auxological characteristics		
Change in weight	From start of Norditropin [®] treatment until end of follow-up	SDS
Change in body mass index (BMI)	From start of Norditropin [®] treatment until end of follow-up	Kg/m ²
Change in bone age	From start of Norditropin [®] treatment until end of follow-up	year
Change in height velocity	From start of Norditropin [®] treatment until end of follow-up	cm/year and SDS/year
Type and number of NS comorbidities	At all visits	NA

Secondary objective-5: To evaluate the evolution of Health-Related Quality of Life (HRQoL) of patients/Legally Acceptable Representative (LAR).

The endpoints related to the secondary objective-5 are listed in [Table 7](#).

Table 7 Secondary endpoint in relation to secondary objective 5

Title of endpoint	Time frame	Unit
Change in HRQoL score (PedsQL)	From start of Norditropin [®] treatment until end of follow-up	NA

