8.7.2 Statistical methods

A descriptive analysis will be conducted on all study endpoints for which data has been collected both on FAS (GAS for primary endpoint) and per subgroups of interest as long as that the sizes of the subgroups are relevant for statistical estimations.

The following statistics will be provided for quantitative variables: number of patients with non-missing and missing values, mean, standard deviation, median, first quartile (Q1), third quartile (Q3), minimum and maximum value, mode (for discrete quantitative variables with limited variability).

For qualitative variables, the number and proportion of each variable modality will be provided together with the number of missing values. Proportions will be computed based on the population with non-missing data. Missing data will not be imputed or replaced.

Exploratory comparison between study subgroups might be considered. Statistical tests will be based on the type and the variables. All comparison tests will be two-tailed with a standard type 1 error threshold of 5% (significance level).

In order to reach the exploratory objectives, logistic regressions will be implemented to identify factors linked to Norditropin[®] growth evolution (reaching height > -2 SDS) and patients' HRQoL. The clinically relevant explanatory variables will be first tested with univariate regression. The selected variables will be processed in the multivariate regression (backward selection) and the odds-ratio with their 95% confidence interval will be used for interpretation when the variable effect is significant (5% threshold for p-value).

In addition, a mixed model will be developed to explore HRQoL scores evolution over the follow-up. Patient effect will be considered as random effect.

The patients will be enrolled in the study over a variable period limited to 24 months. The probability that a patient is included in the cohort is greater when the patient has a higher number of annual visits. This study design therefore presents several biases related to:

- the heterogeneous duration of patients' inclusion which depends on the activity size of each participating site;

- the probability that a patient is included in the cohort which depends on the frequency of annual visits.

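### The PedsQL total is defined as a sum of items, which cannot give the 0–100 score in Table 10 and depends on how many items were answered

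*Protocol*

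**What the plan says.** Protocol section 8.2.10 introduces the instrument: "The PedsQL is a widely used 23-items generic questionnaire". The items fall into four dimensions of 8, 5, 5 and 5 items. Each is answered on a five-point scale from 0 (never a problem) to 4 (almost always a problem), so a high raw answer is bad.

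Two consecutive sentences in that section fix the scoring: "The PedsQL total score is computed as the sum of all the items. Items will be transformed to 0-100 scale", with the direction set so that a higher score is better. The second sentence transforms the items, not the total. No sentence divides the sum by the number of items or by the number answered.

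Table 10 (section 8.3) gives the PedsQL score a range of 0 to 100 and types it as categorical. Table 7 makes change in the score the endpoint for secondary objective 5, without a unit. Table 8 adds a yes/no improvement endpoint. Section 8.7.2 uses HRQoL in a logistic regression and in a mixed model over follow-up.

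On missing data, section 8.2.8.2 says that some is to be expected under routine care, and section 8.7.2 says: "Missing data will not be imputed or replaced".

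**The concern.** The stated rule and the stated range cannot both hold. An analyst who follows section 8.2.10 literally produces a score that contradicts Table 10. One who follows Table 10 must replace the sum with something the protocol does not state.

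The choice of replacement is not neutral. Several formulas give 0–100 and agree when every item is answered, but they part when items are blank. A change score is exposed to this, because a child may answer a different number of items at different visits. Part of the apparent change would then reflect questionnaire completion and not quality of life. The score is the only endpoint for secondary objective 5, and it also feeds the improvement endpoint and both HRQoL models.

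**Working it through.** **Inputs (section 8.2.10 unless noted).** Items: 8 + 5 + 5 + 5 = 23. Raw answers r: 0 to 4, higher worse. Target range (Table 10): 0 to 100. The protocol does not print the item transformation. I take the linear reversal t = 100 − 25r, so that 0 becomes 100, 1 becomes 75 and 4 becomes 0.

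**Step 1: can the plan's 0–100 range be reproduced?** Let S be the raw sum.

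| Reading | Formula | Range | Direction |
|---|---|---|---|
| Sum of transformed items | Σt | 0 to 23 × 100 = 2300 | higher better |
| Sum of raw items | S = Σr | 0 to 23 × 4 = 92 | higher worse |
| Mean of transformed items | Σt / (number answered) | 0 to 100 | higher better |
| Raw sum, reversed and rescaled | 100 × (1 − S/92) | 0 to 100 | higher better |

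Only the last two give the range in Table 10, and the protocol states neither.

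**Step 2: complete questionnaires.** Here Σt = 23 × mean, and 100 × (1 − S/92) equals the mean exactly. The sum differs from the 0–100 score only by a constant factor.

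**Step 3: blank items.** The protocol has no item-level rule. Suppose that blanks are simply left out. Take a child who answers 1 (t = 75) on every item answered:

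| Blank items | Transformed sum | Same, divided by 23 | Rescaled raw sum | Mean of answered items |
|---|---|---|---|---|
| 0 | 75 × 23 = 1725 | 75.0 | 100 × (1 − 23/92) = 75.0 | 75 |
| 1 | 75 × 22 = 1650 | 71.7 | 100 × (1 − 22/92) = 76.1 | 75 |
| 3 | 75 × 20 = 1500 | 65.2 | 100 × (1 − 20/92) = 78.3 | 75 |
| 5 | 75 × 18 = 1350 | 58.7 | 100 × (1 − 18/92) = 80.4 | 75 |

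**Step 4: effect on a change score.** Suppose that this child answers all 23 items at baseline and 18 a year later, with no change in any answer given. The transformed sum changes by 1350 − 1725 = −375, which is −21.7% of its baseline value, or 58.7 − 75 = −16.3 points after division by 23. The rescaled raw sum changes by 80.4 − 75 = +5.4 points. The mean of answered items changes by 0.

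**The case against.** The strongest reply is that this is loose drafting with a clear intention. The target scale is stated in both section 8.2.10 and Table 10, and the two sentences can be read as a raw sum that is then reversed and rescaled. With complete questionnaires, all sensible versions give the same direction of change and the same tests. The categorical label does little harm by itself, since the analyses already treat the score as quantitative. All of this stands for complete questionnaires. It does not settle the rule: the text transforms items and not the total, and the rescaled-sum reading is one of those that shift when items are blank.

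A second reply is that handling of blank items is commonly left to the SAP. That is right, and the absence of such a rule is not the point here. The point is that the protocol did state a scoring formula, and that formula does not give its own range.

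A reader might infer more: that blanks make scores worse, or that one blank voids a questionnaire. The documents support neither. No section counts a blank as zero, and doing so deliberately would sit badly with the no-imputation sentence. That sentence is a general rule on missing data, not a PedsQL scoring rule, so it does not void incomplete questionnaires either. The direction of the shift depends on the reading, as the table shows. Any figure for the share of questionnaires lost would need an item non-response rate and independence between items, and the protocol gives neither. It also plans a mobile application with notifications (section 8.9.2) to limit missing questionnaire data.

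**Conclusion.** The concern holds as a contradiction in the protocol's own scoring rule. The stated sum gives 0–2300, or 0–92 in the wrong direction, where Table 10 requires 0–100. This part needs only the 23 items and the stated response range.

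The consequence for blank items is conditional. It assumes that blanks are left out of the sum and that items are transformed linearly. For the child in the example, five blanks move the score from 75 to 58.7 or to 80.4 on the 0–100 scale, depending on the reading. How often this would happen cannot be judged from the protocol, so no overall bias or loss of data is claimed.

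The reach is limited to the PedsQL change score, the improvement endpoint and the HRQoL models, all in incident patients only. The primary height endpoint is unaffected.

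**What to change.** In section 8.2.10, replace the sum with this definition: each item is reversed and transformed to 0–100, and the total score and each domain score are the mean of the answered items of that scale. State that the SAP sets the minimum number of answered items below which a score is missing. In Table 10, list the PedsQL score as continuous, 0 to 100.

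A mean of answered items fills in no value, so it is compatible with the no-imputation sentence. It does treat the blank items as if they would have averaged the same as the answered ones, which is why a minimum is needed.

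The cost is one sentence in section 8.2.10 and one cell in Table 10. No new data are needed, provided that answers are stored item by item.

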8.3 Variables

Table 10 Variables

Variables	Operational Definition	Measurement
Socio-demographic		
Education	Categorical variable : 
 • Standard education • Education with assistance (special needs assistant, units localized for school inclusion (ULIS classes) and medical and education institute) • Educational measures (physiotherapy, psychomotricity, occupational therapy and speech therapy) 	Endpoints
School (education) level	Categorical variable : 
 • Preschool • Elementary school • Secondary school • High school 	Endpoints
Educational measures	Categorical variable : 
 • Physiotherapy • Psychomotricity • Occupational therapy • Speech therapy 	Endpoints
Age of puberty	Continuous variable	Endpoints
Age of onset of menstruations (female only)	Continuous variable	Endpoints
Tanner stage	3 sub-scales : Pubic hair scale (both females and males) Female breast development scale (for females only) Male external genitalia scale (male only) Categorical variable : 
 • Stage 1 • Stage 2 • Stage 3 • Stage 4 • Stage 5 	Endpoints
Clinical		
Comorbidities of interest not related to NS	Categorical variable	Endpoints
Pulse rate	Continuous variable	Endpoints
Diastolic pressure	Continuous variable	Endpoints
Systolic pressure	Continuous variable	Endpoints

Variables	Operational Definition	Measurement
Echocardiogram (left ventricular interventricular septal maximum thickness in diastole, left ventricular end diastolic diameter, LVFS, LVEF and diastolic function (Ea and Aa))	Continuous variable	Endpoints
corrected QT interval	Continuous variable	Endpoints
Complete blood count (CBC) (Hb, white blood cells, lymphocytes, monocytes and platelets)	Continuous variable	Endpoints
IGF-1 level	Continuous variable	Endpoints
IGFBP- 3 level	Continuous variable	Continuous variable
TSH	Continuous variable	Continuous variable
FT4	Continuous variable	Continuous variable
HbA _{1c} level	Continuous variable	Endpoints
Fasting insulin blood level	Continuous variable	Endpoints
Fasting glucose blood level	Continuous variable	Endpoints
Fasting total cholesterol	Continuous variable	Endpoints
Fasting triglycerides	Continuous variable	Endpoints
Fasting HDL level	Continuous variable	Endpoints
Fasting LDL level	Continuous variable	Endpoints
Fasting ratio total cholesterol/ HDL level	Continuous variable	Endpoints
Inhibin-B	Continuous variable	Endpoints
AMH	Continuous variable	Endpoints
LH	Continuous variable	Endpoints
FSH	Continuous variable	Endpoints
Oestradiol	Continuous variable	Endpoints
Testosterone	Continuous variable	Endpoints
Auxology		
Gestational age at birth	Continuous variable	Endpoints
Head circumference at birth , at 1 year, 2 years and 3 years of age	Continuous variable	Endpoints
Birth weight, at 1 year, 2 years and 3 years of age	Continuous variable	Endpoints
Birth length at 1 year, 2 years and 3 years	Continuous variable	Endpoints
Weight at start of Norditropin®	Continuous variable	Endpoints

Variables	Operational Definition	Measurement
Height at start of Norditropin®	Continuous variable	Endpoints
Parents 'height	Continuous variable	Endpoints
BMI	Continuous variable	Endpoints
Height velocity in the first year/6 months preceding Norditropin® treatment start	Continuous variable	Endpoints
Height velocity	Continuous variable	Endpoints
Adult height (AH)	Continuous variable	Endpoints
Bone age	Continuous variable	Endpoints
Diagnosis		
Familial form of Noonan	Categorical variable 
 • Yes • No 	Endpoints
Parent affected (if yes to familial form of Noonan)	Categorical variant 
 • Mother • Father 	
Age at clinical diagnosis of NS	Continuous variable	Endpoints
Molecular diagnosis performed	Categorical variable 
 • Yes • No 	
Date of molecular diagnosis of NS (if yes to molecular diagnosis performed)	Continuous variable	Endpoints
Molecular diagnosis (type of NS-related genes mutated and variant identified)	Categorical variable 
 • PTPN1 • KRAS • RAF1 • RIT1 • SHOC2 • SOS1 • SOS2 • Other 	Endpoints
NS comorbidities		
NS comorbidities	Categorical variable 
 • Cardiac defects including pulmonary valve stenosis and hypertrophic cardiomyopathy • Orthopaedic issues (pectus, scoliosis) • Anorchia in males 	Endpoints
Therapeutic care		
Dose of Norditropin® treatment	Continuous variable Recorded at each study visit	Endpoints

Variables	Operational Definition	Measurement
Total duration of Norditropin® treatment	Continuous variable From start of Norditropin® treatment until end of follow-up	Endpoints
Total cumulative of Norditropin® dose	Continuous variable Total dose of Norditropin® administered from start of treatment until end of treatment	Endpoints
Frequency of injections per week	Categorical variable 
 • 6 days/7 • 7 days/7 • Other 	Endpoints
Type of treatment modifications	Categorical variable 
 • Increase in dosage • Decrease in dosage • Temporary stop • Permanent stop 	Endpoints
Duration of temporary stop	Continuous variable	Endpoints
Number of treatment modifications	Categorical variable 
 • From 1 to 5 	Endpoints
Reasons for treatment modifications	Categorical variable 
 • Safety (occurrence of ARs or AEs) • Growth too fast • Growth too slow • Patient's or parents/LAR choice • Other 	Endpoints
Type of previous GH treatments	Categorical variable	Endpoints
Dose of previous GH treatment at start	Continuous variable	Endpoints
Total duration of previous GH treatment	Continuous variable From start of previous GH treatment until the end of treatment	Endpoints
Type of GH treatment following Norditropin®	Categorical variable	Endpoints
Dose of GH treatment following Norditropin®	Continuous variable	Endpoints
Date of GH treatment following Norditropin®	Continuous variable	Endpoints
Concomitant medications	Categorical variable 
 • ADHD medications including methylphenidate • Cardiac medications • Thyroid hormones • Sex steroids including testosterone and oestrogen 	Endpoints

Variables	Operational Definition	Measurement
	
 Other 	
HRQoL		
PedsQL score	Categorical variable 
 From 0 to100 	Endpoints
Safety		
Incidence rate	Number of new cases per population at risk over the follow-up period (per person-time)	Endpoints
Other co-variates (controls)		
Sites 'geographic location	Categorical variable : 
 Ile-De France North-West West East South-East South-West 	Bias
Sites 'activity size s	Continuous variable Defined by the number of children treated with Norditropin® for short stature due to NS managed over a year	Bias

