8.1.1.2 Secondary endpoints

Secondary objective-1: To evaluate the long-term safety profile of Norditropin®.

All drug related adverse reactions (ADR), serious adverse drug reactions (SADR), serious adverse events (SAE) and adverse events (AE) will be recorded and described up to the end of growth development or end of follow-up if earlier. The endpoints related to the secondary objective-1 are listed in [Table 3](#).

Table 3 Secondary endpoints in relation to secondary objective 1

Title of endpoint	Time frame	Unit
Number of adverse drug reactions (ADR)	From start of Norditropin® until end of follow-up	Count of events
Number of serious adverse drug reactions (SADR),	From start of Norditropin® until end of follow-up	Count of events
Number of serious adverse events (SAE)	From start of Norditropin® until end of follow-up	Count of events
Number of adverse events (AE)	From start of Norditropin® until end of follow-up	Count of events

Secondary objective-2: To describe the socio-demographic and clinical characteristics of patients. The endpoints related to the secondary objective-2 are listed in [Table 4](#).

Table 4 Secondary endpoints in relation to secondary objective 2

Title of endpoint	Time frame	Unit
Socio-demographic		
Education	From start of Norditropin® treatment until end of follow-up	NA
School level	From start of Norditropin® treatment until end of follow-up	NA
Educational measures	From start of Norditropin® treatment until end of follow-up	NA
Clinical characteristics		

Title of endpoint	Time frame	Unit
Tanner stage	At all visits	NA
Change in pulse rate	From start of Norditropin® treatment until end of follow-up	Beats per minute
Change in diastolic blood pressure	From start of Norditropin® treatment until end of follow-up	mm Hg
Change in systolic blood pressure	From start of Norditropin® treatment until end of follow-up	mm Hg
Change in corrected QT-interval (Electrocardiogram)	From start of Norditropin® treatment until end of follow-up	msec
Change in echocardiogram parameters	From start of Norditropin® treatment until end of follow-up	mm (Left ventricular interventricular septal maximum thickness in diastole) mm (Left ventricular end diastolic diameter) % (Left Ventricular Fractional Shortening (LVFS)) % (Left Ventricular Ejection Fraction (LVEF)) Cm/s (Diastolic function (Ea)) Cm/s (Diastolic function (Aa))

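### Table 10 lists a set of therapies as a third level of Education, overlapping both types of schooling, so the shares in standard and assisted education are not well defined

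*Protocol*

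**What the plan says.** Section 8.3, Table 10, gives Education as a categorical variable with three levels:

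- "Standard education"
- "Education with assistance (special needs assistant, units localized for school inclusion (ULIS classes) and medical and education institute"), that is, assisted schooling
- "Educational measures (physiotherapy, psychomotricity, occupational therapy and speech therapy")

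The same table has a separate categorical variable for educational measures, whose levels are those same four therapies. Section 8.1.1.2, Table 4, lists Education and educational measures as two endpoints of secondary objective 2, each followed from treatment start to end of follow-up. The flow chart in section 8.2.8.1 also names them as distinct items, "Education, school level and educational measures", collected at baseline and at every follow-up visit.

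For qualitative variables, section 8.7.2 states that "the number and proportion of each variable modality will be provided together with the number of missing values", with proportions taken over patients with non-missing data.

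The protocol does not say whether Education takes one answer or several. It gives no order of priority for a child who fits two levels.

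**The concern.** A list of levels gives an interpretable distribution when each child belongs to exactly one level, or when the item is declared to accept several answers. Here neither holds. The first two levels say where or how the child is schooled; the third says what therapy the child receives. A child in standard school who has speech therapy fits levels 1 and 3. A child in a ULIS class who has physiotherapy fits levels 2 and 3.

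At stake is what the reported percentages mean. If a site enters such a child only under level 3, the type of schooling is not recorded in this variable, and no later analysis of it can restore it. Because the item is repeated at each visit, a child who starts a therapy without changing school could then appear to have left standard or assisted education. Section 8.5 expects about 30 participating sites, and part of the data will be taken retrospectively from medical records. Without a rule, sites may resolve the overlap differently.

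**Working it through.** **Comparison of the passages**

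1. Table 10, Education: levels 1 and 2 are types of schooling, and level 3 is four therapies.
2. Table 10, educational measures: the same four therapies, as a variable of their own.
3. Table 4 and the flow chart: Education and educational measures are separate items.
4. Section 8.7.2: one proportion is reported per level.

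Items 2 and 3 show that the therapy information is already collected elsewhere, so level 3 of Education is a duplicate. Items 1 and 4 show that a proportion will be reported for levels that overlap.

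**What each coding would give**

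The protocol states no figure for this variable, so there is nothing to reproduce. Let *s* be the true share in standard education and 1 − *s* the share in assisted education. Let *t* be the fraction receiving at least one listed therapy, taken as equal in both groups. The values of *s* and *t* below are assumptions; the protocol gives neither.

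- **Single choice, therapy children entered under level 3:** standard = *s*(1 − *t*); assisted = (1 − *s*)(1 − *t*); level 3 = *t*. These sum to 1.
- **Single choice, therapy children kept under their type of schooling:** standard = *s*; assisted = 1 − *s*. There is no error in either share.
- **Multi-response:** standard = *s*; assisted = 1 − *s*; level 3 = *t*. These sum to 1 + *t*.

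| Assumed *s* | Assumed *t* | Standard, single choice under level 3 | Assisted, single choice under level 3 | Sum of levels, multi-response |
|---|---|---|---|---|
| 50% | 10% | 0.50 × 0.90 = 45% | 0.50 × 0.90 = 45% | 110% |
| 50% | 30% | 0.50 × 0.70 = 35% | 0.50 × 0.70 = 35% | 130% |
| 50% | 50% | 0.50 × 0.50 = 25% | 0.50 × 0.50 = 25% | 150% |
| 70% | 10% | 0.70 × 0.90 = 63% | 0.30 × 0.90 = 27% | 110% |
| 70% | 30% | 0.70 × 0.70 = 49% | 0.30 × 0.70 = 21% | 130% |
| 70% | 50% | 0.70 × 0.50 = 35% | 0.30 × 0.50 = 15% | 150% |

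The same data can therefore give a standard-education share of *s* or of *s*(1 − *t*), depending on a coding choice that the protocol does not make. With level 3 deleted, the two shares are *s* and 1 − *s* whatever *t* is, and they sum to 100%.

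**The case against.** The strongest objection is that single choice is an assumption. Table 10 applies the same label, categorical variable, to lists whose entries can occur together in one child: comorbidities of Noonan syndrome and concomitant medications. Tables 5 and 6 ask for the type and number of these, so several entries per child are expected there. If Education is read in the same way, the standard and assisted shares are correct. The case report form and data management plan, which may settle the matter, are not at hand. This stands, and it rules out four stronger readings that a reader might infer:

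- *The share in standard education is miscounted.* This needs single choice and, in addition, entry of such children under level 3. The protocol states neither.
- *The separate therapy variable cannot hold two therapies in one child.* This also presumes single choice.
- *Children with no therapy drop out of the denominator as missing.* The therapy list has no entry for none, but neither do the comorbidity and medication lists. Section 8.7.2 does not say that absence of therapy is stored as missing.
- *The therapy percentages must add up to 100% whatever the uptake.* This needs both single choice and storage of no therapy as missing.

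The objection does not remove the overlap. Table 10 presents these levels as the operational definition, so this is a stated list and not a detail left to a later document. Even under the multi-response reading, level 3 is redundant and the levels of Education sum to more than 100% whenever any child receives a therapy.

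**Conclusion.** The point holds as an ambiguity in a stated definition. The third level of Education overlaps the other two and duplicates a separate endpoint. No coding rule is given, so the shares in standard and in assisted education are not well defined. They would be understated under single-choice entry of therapy children at level 3, by a proportion equal to the therapy fraction in each group, and unaffected under multi-response coding.

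The actual size cannot be derived from the protocol; the percentages worked above only illustrate the range under assumed rates. The importance is minor. Education is one of many descriptive characteristics under secondary objective 2, and neither the primary endpoint nor the precision calculation in section 8.5 depends on it.

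**What to change.** In Table 10, delete the third level so that Education has two: standard, and with assistance. Keep the four therapies only in the separate educational measures variable. Declare that variable multi-response, and state that children receiving no therapy count in the denominator. This last statement is a clarification that settles a point on which the protocol is silent.

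The cost is a change to two rows of Table 10 and, if the electronic form follows the present list, to one answer list. No extra data are needed, because the therapies are already collected separately at every visit.
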